Study Duration	Screening/baseline for up to 21 days. Dosing typically for 22 to 48 weeks, unless double-blind treatment is extended for subjects waiting for activation of follow-on protocols. Up to 6 months (or more) additional observational follow-up for subjects terminating early for GI AEs.

Protocol ARC007 Amendment 2.0 Synopsis	
Title	REAL-WORLD AR101 MARKET-SUPPORTING EXPERIENCE STUDY IN PEANUT-ALLERGIC CHILDREN AGES 4 TO 17 YEARS
Primary Endpoint	The primary endpoint of this study is the frequency of treatment-emergent AEs, including serious AEs, during the overall study period.
Secondary Endpoints	
Secondary Endpoints
 
 Frequency of premature discontinuation of dosing due to AEs Frequency of premature discontinuation of dosing due to chronic/recurrent GI AEs Proportion of chronic / recurrent GI AEs resolving at 2, 4, and \geq 12 weeks following cessation of dosing Frequency of allergic reaction (hypersensitivity) AEs occurring during up-dosing, normalized for duration of treatment Frequency of anaphylaxis as defined in the protocol Frequency of use of epinephrine as a rescue medication Frequency of accidental ingestions of peanut and other allergenic foods and severity of any resultant reactions Assessment of asthma control using the Asthma Control Test (ACT) questionnaire and frequency of use of asthma rescue medication (short acting beta-agonists) in subjects with asthma
Exploratory Endpoints	
Exploratory Endpoints
 
 Changes in peanut-specific and peanut component-specific serum immunoglobulin E (IgE) and immunoglobulin G subclass 4 (IgG₄) levels Changes in peanut skin prick test (SPT) mean wheal diameter Changes in Total Nasal Symptom Score in subjects with allergic rhinitis Changes in scores of the food allergy related quality of life questionnaire (FAQLQ) and food allergy independent measure (FAIM) questionnaire

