1. BACKGROUND AND RATIONALE

1.1 Background

Peanut allergy is a common and serious condition that disproportionately affects children and is associated with severe reactions, including life-threatening anaphylaxis. The prevalence of peanut allergy, like other food allergies, has been rising, and is now at high levels, affecting up to 2% of the population (Sicherer and Sampson 2014). The current standard of care in management of peanut allergy is a peanut-avoidant diet, along with education of the patient and family in the acute management of an allergic reaction, including ready access to self-injectable epinephrine. The burden of avoidance and the constant fear of accidental exposure negatively affect the health-related quality of life for patients and their families (Primeau et al, 2000; Avery et al, 2003; Sicherer et al, 2010; Anagnostou et al, 2014).

In addition, peanut-avoidant diets are complicated by the difficulty of interpreting food labels and the presence of undeclared or hidden allergens in commercially-prepared foods (Joshi et al, 2002; Altschul et al, 2001; Vierk et al, 2002). Accidental exposures are common, with 55 percent of food-allergic patients having at least 1 allergic reaction in a 5-year period (Sicherer et al, 1998).

In early clinical trials, oral immunotherapy (OIT) for peanut allergy has demonstrated encouraging safety and efficacy results in creating a change in clinical reactivity that would protect recipients from these accidental exposures (Jones et al, 2009; Hofmann et al, 2009; Blumchen et al, 2010; Yu et al, 2012; Varshney et al, 2011; Anagnostou, et al 2014). All of these studies involved a period of up-dosing with increasing amounts of peanut protein, a period of maintenance therapy, and then an oral food challenge to assess desensitization. Dosing symptoms observed in these studies included rash, wheezing, rhinorrhea, sneezing, itching, abdominal pain, nausea, vomiting, and diarrhea. Most symptoms were mild, consistent with a transient, low-grade allergic reaction, and tended to diminish in frequency with increasing duration of treatment.

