## 7 DEFINITIONS, DERIVATIONS, AND CONVENTIONS

### 7.1 Definitions and Derivations

- Study day is calculated as (assessment date – first dose date + 1) for assessments and visits performed on or after the first dose date, and (assessment date – first dose date) for assessments and visits prior to the first dose date.
- Baseline is defined as the last nonmissing value prior to the first dose of randomized study treatment in ARC007.
- Change from baseline is calculated as the observed value after the first dose – baseline value.
- The screening period is defined as the time beginning with the date and time of informed consent through the day prior to randomization.
- Initial escalation is defined as the time beginning with the date and time of the first dose of randomized study product at the study site and ending with the date of the last dose of randomized study product taken prior to up-dosing.
- Up-dosing is defined as the time beginning with the date and time of the first dose of study product at 3 mg at home, and ending with the date and time of first dose at

300 mg at the study site. Up-dosing will be approximately 20 weeks in duration, but may be extended to a maximum of 40 weeks to accommodate dose reductions and re-escalations, if necessary.

- A 300 mg QD period will be defined as the time beginning with the date and time of the first dose of study product at 300 mg at home and ending with the date of the last dose of study product. This period will be ideally approximately 2 weeks in duration at the end of ARC007, but dosing may continue up to a maximum of 48 weeks after day 1 to ensure tolerability of 300 mg prior to exiting ARC007. Some subjects continued to receive 300 mg doses in ARC007 after the expected rollover date while waiting for activation of ARC008 or ARC011 at the study site. The 300 mg doses as a result of the rollover delay will be included in the 300 mg QD period.

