### 9.5 Extent of Exposure and Compliance

Study treatment exposure will be summarized for the safety population by age group (4-11 years, 12-17 years, 4-17 years), treatment group (AR101, placebo) and study period (initial escalation, up-dosing, 300 mg QD, and overall).

First and last dose dates for each study period will be identified as follows:

Study Period	First Dose Date	Last Dose Date
Initial escalation	Date of first dose at the study site on initial escalation day 1	Date of last dose at initial escalation day 1 or day 2 at the study site
Up-dosing	The day following the date study product was dispensed at initial escalation day 2	Date of first dose of 300 mg at the end of the up-dosing 300 mg visit if dose is tolerated and subject continues to at-home 300 mg QD dosing. If first in-clinic 300 mg dose is not tolerated and dose is immediately reduced, the last dose date of up-dosing will be when the first in-clinic 300 mg dose is tolerated and subject continues to at-home 300 mg QD dosing. For subjects who do not reach the 300 mg dose, the latest of the last dose during up-dosing at the study site and the last dose at home
300 mg QD	Date of first dose of study product of 300 mg at home. This is defined as the day following the first in-clinic visit where the 300 mg dose was tolerated and 300 mg study product was first dispensed.	Date of last dose of study product for subjects who enter 300 mg QD study period
Overall	Date of first dose at the study site on initial escalation day 1	Last dose of study product prior to exit visit in ARC007

The total amount of study product consumed will be calculated as the sum of doses at the study site plus the sum of doses taken at home as recorded in the dosing diary.

The following calculations of study product exposure will be made and summarized:

- Duration of exposure (in days and in months): calculated as the date of the last dose of study product minus the date of the first dose of study product plus 1 during the study period, except for initial escalation, the duration of exposure will only be 1 or 2 days depending on whether study product was taken on initial escalation day 1 and initial escalation day 2. Duration of exposure will be summarized using descriptive statistics for continuous endpoints and categorically by 28-day increments for the overall treatment period:  $\leq 28$  days, 29–56 days, ... 337–364 days, and  $> 364$  days.

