- Overall summary of number of unique treatment-emergent adverse events and treatment-emergent serious adverse events, subject incidence of treatment-emergent adverse events and treatment-emergent serious adverse events meeting various criteria, and exposure-adjusted incidence rates of treatment-emergent adverse events and treatment-emergent serious adverse events meeting various criteria, where exposure incidence rates are defined as the total number of events divided by the total number of subject-years at risk; the total number of subject-years at risk is defined as total number of days for all subjects in the study period divided by 365.25.
- Subject incidence of treatment-emergent adverse events by SOC and preferred term.
- Subject incidence of treatment-emergent adverse events by preferred term.
- Exposure-adjusted event rates for the most frequent treatment-emergent adverse events (ie, treatment-emergent adverse events occurring in  $\geq 5\%$  of the safety population) by preferred term.
- Subject incidence of treatment-emergent adverse events by severity grade, SOC, and preferred term.
- Subject incidence of treatment-emergent adverse events related to study product by SOC and preferred term.
- Exposure-adjusted event rates for the most frequent treatment-emergent adverse events related to study product (ie, related treatment-emergent adverse events occurring in  $\geq 5\%$  of the safety population) by preferred term.
- Subject incidence of grade  $\geq 3$  severity treatment-emergent adverse events by SOC and preferred term.
- Subject incidence of grade  $\geq 3$  severity treatment-emergent adverse events related to study product by SOC and preferred term.
- Subject incidence of serious adverse events by SOC and preferred term.
- Subject incidence of treatment-emergent adverse events leading to discontinuation of study product by SOC and preferred term.
- Subject incidence of treatment-emergent adverse events associated with the use of epinephrine by SOC and preferred term.
- Subject incidence of hypersensitivity treatment-emergent adverse events by SOC and preferred term, where hypersensitivity treatment-emergent adverse events are those treatment-emergent adverse events from the allergic adverse event and in-clinic dosing case report forms.

- Subject incidence of hypersensitivity treatment-emergent adverse events related to study product by SOC and preferred term.

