- Exposure-adjusted event rates for hypersensitivity treatment-emergent adverse events by preferred term.
- Subject incidence of treatment-emergent adverse events associated with a non-study product food allergen exposure by SOC, and preferred term.
- Subject incidence of treatment-emergent adverse events leading to early discontinuation by SOC and preferred term.
- Subject incidence of treatment-emergent adverse events with onset < 90 minutes after study product dosing at the study site by SOC and preferred term.

At each level of summarization (eg, any adverse event, SOC, and preferred term), subjects experiencing more than 1 treatment-emergent adverse event will be counted only once within each study period. In the summary of treatment-emergent adverse events by severity grade, subjects will be counted once at the highest severity reported at each level of summarization. Adverse event data will be presented in data listings by age group, treatment group, subject, study period, and event. Treatment-emergent adverse events; serious adverse events; severe, life-threatening, or fatal adverse events; and adverse events leading to discontinuation, reduction, or interruption of the study product will be presented in separate data listings.

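### The duration-normalised up-dosing reaction rate divides by time that itself depends on reactions, so the two arms' rates may not be comparable, and the direction of any distortion is not fixed

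*Protocol*

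**What the plan says.** The Protocol synopsis and Section 9.2.2 list as a secondary endpoint "Frequency of allergic reaction (hypersensitivity) AEs occurring during up-dosing, normalized for duration of treatment", and SAP 4.2 carries it over. SAP 9.8.1 states how rates are formed: "exposure incidence rates are defined as the total number of events divided by the total number of subject-years at risk", where subject-years are the "total number of days for all subjects in the study period divided by 365.25". The output for this endpoint is "Exposure-adjusted event rates for hypersensitivity treatment-emergent adverse events by preferred term", shown by arm, age group and study period.

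On the length of up-dosing, SAP 7.1 gives about 20 weeks and adds that it "may be extended to a maximum of 40 weeks to accommodate dose reductions and re-escalations". Protocol 6.3.3 resets the escalation schedule after a dose reduction, and it stops dosing after three consecutive failed escalation attempts. Protocol 6.5.6 describes 6 to 8 weeks at a reduced dose after a second consecutive epinephrine use at escalation. Protocol 6.5.3.2 describes a 4-week suspension for certain gastrointestinal symptoms.

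SAP 9.5 measures exposure by calendar span ("calculated as the date of the last dose of study product minus the date of the first dose of study product plus 1"), with no deduction for withheld days outside initial escalation. SAP 9.8.1 mentions no deduction either.

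On time trend, the only statement is in Protocol 1.1: in earlier oral immunotherapy studies most symptoms were mild and "tended to diminish in frequency with increasing duration of treatment".

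**The concern.** A pooled events-per-subject-year rate compares two groups fairly if the event rate is constant over time and unrelated to how long each child is followed, or if both groups have the same pattern of follow-up. Here the follow-up time is partly a result of the events being counted. Reactions lead to dose reductions, reductions lengthen up-dosing, and repeated failure ends it. These effects should fall mainly on the AR101 arm.

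Three mechanisms can then move the AR101 rate away from what a common time window would show:
- Extra late weeks add denominator. If rates fall with time, they add few events.
- If the extended children are the more reactive ones, pooling by time gives them more weight.
- Early stopping removes time from whichever children stop.

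These can pull in opposite directions. At stake is whether a reader can interpret the two arms' rates side by side. No planned table gives reaction rates by time since the start of up-dosing or over a common window.

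**Working it through.** The documents give no reaction rate, event count or ratio for this endpoint, so there is no figure to reproduce. One design check: Protocol Table 2 has ten dose levels below 300 mg at 2 weeks each, and 10 × 2 = 20 weeks, which matches the stated minimum.

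Inputs from the documents: up-dosing of 20 to 40 weeks; 21% early discontinuation on AR101 in the earlier trial (6 of 29, Protocol Appendix 7); a possible 4-week suspension. Everything else below is assumed.

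**1. All AR101 children share one declining rate.** Let the rate be r₀·exp(−kt) with k = ln 2 / half-life. The mean rate over T weeks, in units of r₀, is m(T) = (1 − e^(−kT)) / (kT). If placebo takes 20 weeks, the AR101-to-placebo ratio is multiplied by m(T)/m(20). For a 20-week half-life and T = 24: 0.6789 / 0.7213 = 0.94.

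| Half-life | T = 24 | T = 30 | T = 40 |
|---|---|---|---|
| constant rate | 1.00 | 1.00 | 1.00 |
| 40 weeks | 0.97 | 0.92 | 0.85 |
| 20 weeks | 0.94 | 0.86 | 0.75 |
| 10 weeks | 0.90 | 0.78 | 0.63 |

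If the rate instead doubles every 40 or 20 weeks, T = 24 gives 1.04 or 1.08.

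**2. The extended children are more reactive.** Suppose 30% react at 3 times the rate and take 30 weeks, and the rest take 20. With constant rates:
- pooled rate = (0.3×3×30 + 0.7×20) / (0.3×30 + 0.7×20) = 41/23 = 1.783
- mean rate per child = 0.3×3 + 0.7 = 1.6
- factor = 1.783/1.6 = 1.11, an overstatement

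For half-lives of 40, 20 and 10 weeks the factor is 1.06, 1.01 and 0.95.

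**3. Add early stopping.** Let 21% stop at week 6 and keep 30% extended to 30 weeks at 3 times the rate. If the stoppers also react at 3 times the rate, the factor is 0.90 to 1.00. If they react at the baseline rate, it is 1.02 to 1.19. Both ranges run from a 10-week half-life to a constant rate.

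**4. Combined scenario, true ratio 3.0 at every week.** Assumed: 40% of AR101 non-stoppers extended uniformly over 20 to 40 weeks; 0% or 21% of AR101 stopping uniformly over weeks 0 to 20; both groups 1 or 2 times as reactive, rescaled so the arm average stays at 3; 95% of placebo finishing at week 20; rate proportional to exp(−t/τ), so expected events to T are τ(1 − e^(−T/τ)).

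Example with τ = 10, no stopping, equal reactivity, and the other 5% of placebo extended. Events to week 20 are 8.647; averaged over the extended children they are 9.415.
- AR101: (0.4×9.415 + 0.6×8.647)/24 = 0.3731
- placebo: (0.05×9.415 + 0.95×8.647)/20.5 = 0.4237
- ratio = 3 × 0.3731/0.4237 = 2.64

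Example with constant rates, 2 times the reactivity and no stopping: 3 × [(0.4×2×30 + 0.6×20)/1.4]/24 = 3.21.

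| Assumption on rate | Pooled ratio (true 3.0) |
|---|---|
| τ = 5 to 20, other placebo 5% stop early | 2.48 to 2.79 |
| τ = 5 to 20, other placebo 5% extended | 2.58 to 2.85 |
| τ = 40, 2× reactive, no stopping (placebo 5% extended) | 2.99 |
| constant, equal reactivity | 3.00 |
| constant, 2× reactive, 21% or 0% stopping | 3.05 or 3.21 |
| rising, 40-week constant (placebo 5% extended) | 3.17 to 3.54 |

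The first two rows span 1 − 2.85/3 = 5% to 1 − 2.48/3 = 17% too low. Mean cumulative events to week 20, built from 4-week interval rates, give 2.91 to 3.01 for τ = 5 to 20. The low end occurs when 21% stop and those children are twice as reactive.

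**5. Withheld days.** A child with 24 weeks of up-dosing, 4 of them withheld, has a rate lower by 4/24 = 17% than the same count over the 20 on-dose weeks.

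**The case against.** The SAP does what the endpoint says: it divides by duration. No formal test or comparison between arms is planned (Protocol Section 9), and this is one of eight protocol secondary endpoints, with anaphylaxis and epinephrine use reported separately. The SAP also plans "Subject incidence of hypersensitivity treatment-emergent adverse events by SOC and preferred term", symptom summaries by dose level (9.8.6, 9.8.7), and exposure duration, dose-reduction counts and time to 80 and 300 mg (9.5). Unequal duration between arms would therefore be visible.

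This lowers the impact but does not remove the point. Subject incidence counts a child once per period. The dose-level tables give numbers of children and maximum severity, and the in-clinic table adds symptom timing. None of them is an event rate over a common time. The arms are tabulated side by side in a placebo-controlled study, so readers will compare them.

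A reader might go further and infer that the AR101 rate is understated and that the bias favours the product. The documents do not support that. It needs a decline within up-dosing, and the only evidence is one qualitative background sentence about earlier studies that also included maintenance. In this trial the dose rises from 3 to 300 mg over the same period, so a flat or rising rate is not excluded. It is also tempting to say that constant rates would remove any distortion; step 2 shows they do not if the extended children are the more reactive ones.

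A week-20 cumulative count has its own weakness. It cuts off later high-dose reactions in children whose escalation was delayed, and it remains affected by informative dropout.

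**Conclusion.** The point holds as a problem of interpretation. The only duration-normalised measure pools over time that depends on reactions, and it keeps withheld days in the denominator. The two arms' rates can therefore be distorted in either direction.

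Understatement for AR101 is plausible, at about 5% to 17% with decay constants of 5 to 20 weeks and the assumed extension and dropout patterns. Overstatement is possible, at about 2% to 7% (3.05 to 3.21 against 3.0) with constant rates and extended and early-stopping children twice as reactive, and more if rates rise. These sizes rest on assumptions about extension, stopping, reactivity and time trend that the documents do not supply. The gap warrants an inexpensive addition to the SAP; it does not invalidate a planned comparison.

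**What to change.** In SAP 9.8.1, keep the pooled rate and add one table by arm for hypersensitivity TEAEs in up-dosing, giving:
- events and subject-weeks at risk by 4-week interval since the first home dose (weeks 1–4 to 17–20, then 21–40);
- mean cumulative events per child, to week 20 and through the end of up-dosing;
- the number of children who discontinued in each interval;
- a sensitivity rate with on-dose days as the denominator.

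All of this uses dates and diary records already collected, and nothing in trial conduct changes. The cost is SAP wording and one extra table. Few placebo children will contribute after week 20, so that interval will be imprecise. Given the limits of the week-20 count noted above, it should supplement the pooled rate and not replace it.

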FDA	US Food and Drug Administration
FEV ₁	forced expiratory volume in 1 second
GCP	Good Clinical Practice
GERD	gastroesophageal reflux disease
GI	gastrointestinal

ICH	International Council for Harmonisation
ICF	informed consent form
ICS	inhaled corticosteroid
lgE	immunoglobulin E
lgG ₄	immunoglobulin G subclass 4
IND	Investigational New Drug
IP	investigational product
IRB	institutional review board
ITT	intent-to-treat
IV	intravenous
IXRS	interactive voice/web response system
NCI-CTCAE	National Cancer Institute Common Terminology Criteria for Adverse Events
NHLBI	National Heart, Lung, and Blood Institute
OIT	oral immunotherapy
PEESS	Pediatric Eosinophilic Esophagitis Symptom Scores
PEFR	peak expiratory flow rate
PR	pulse rate
PRACTALL	PRACTical issues in ALLergology Joint United States/European Union
qPCR	quantitative polymerase chain reaction
RNA	ribonucleic acid
SAE	serious adverse event
SAP	Statistical Analysis Plan
SOE	schedule of events
SPT	skin prick test
SVM	support vector machine
TEAE	treatment-emergent adverse event

1. BACKGROUND AND RATIONALE

1.1 Background

Peanut allergy is a common and serious condition that disproportionately affects children and is associated with severe reactions, including life-threatening anaphylaxis. The prevalence of peanut allergy, like other food allergies, has been rising, and is now at high levels, affecting up to 2% of the population (Sicherer and Sampson 2014). The current standard of care in management of peanut allergy is a peanut-avoidant diet, along with education of the patient and family in the acute management of an allergic reaction, including ready access to self-injectable epinephrine. The burden of avoidance and the constant fear of accidental exposure negatively affect the health-related quality of life for patients and their families (Primeau et al, 2000; Avery et al, 2003; Sicherer et al, 2010; Anagnostou et al, 2014).

In addition, peanut-avoidant diets are complicated by the difficulty of interpreting food labels and the presence of undeclared or hidden allergens in commercially-prepared foods (Joshi et al, 2002; Altschul et al, 2001; Vierk et al, 2002). Accidental exposures are common, with 55 percent of food-allergic patients having at least 1 allergic reaction in a 5-year period (Sicherer et al, 1998).

In early clinical trials, oral immunotherapy (OIT) for peanut allergy has demonstrated encouraging safety and efficacy results in creating a change in clinical reactivity that would protect recipients from these accidental exposures (Jones et al, 2009; Hofmann et al, 2009; Blumchen et al, 2010; Yu et al, 2012; Varshney et al, 2011; Anagnostou, et al 2014). All of these studies involved a period of up-dosing with increasing amounts of peanut protein, a period of maintenance therapy, and then an oral food challenge to assess desensitization. Dosing symptoms observed in these studies included rash, wheezing, rhinorrhea, sneezing, itching, abdominal pain, nausea, vomiting, and diarrhea. Most symptoms were mild, consistent with a transient, low-grade allergic reaction, and tended to diminish in frequency with increasing duration of treatment.

There is evidence that OIT induces a clinically meaningful level of desensitization in most patients and may also induce favorable immunologic changes over time. Though these studies used different doses and regimens, they collectively provide supportive evidence for the efficacy and safety of peanut OIT and were the basis for the initiation of clinical development of AR101, a standardized OIT product manufactured to pharmaceutical-grade standards and previously tested in Aimmune's Phase 2 program and ongoing Phase 3 programs.

The goal of OIT with AR101 is to induce and maintain a state of desensitization to peanut protein, defined as the ability to consume a specific dose of peanut protein with no or mild symptoms. This state of desensitization, in conjunction with a peanut-avoidant diet, should be sufficient to protect a peanut-allergic individual from an accidental exposure to peanuts or peanut-containing foods.

